Reference Therapy, Dose and Duration of Administration: 
Those subjects randomised to the placebo arm will be administered matching placebo capsules that are indistinguishable to the test product in appearance and taste but contain no active ingredient.
 
All doses should be taken orally by the subject, with water, on a weekly basis (± 1 day from the time schedule of regular planned dose) at approximately the same time of the day.
		
Duration of Treatment: 
All subjects will be treated with BGS649 or matched placebo for a maximum of 24 weekly doses (which provides 24 weeks therapeutic coverage due to long half-life of BGS649). Some subjects who complete 24 weeks of treatment will be invited to participate in a 6-month blinded safety extension study (Protocol MBGS206). An interim analysis will be performed once approximately 100 of overall planned enrolled subjects have completed the Week 4 visit and any doses of BGS649 that did not lead to normalisation of testosterone or were considered unsafe will be identified and the dose arm terminated.
		

Name of Sponsor/Company: Mereo BioPharma 2 Ltd	Individual Study Table Referring to Part of the Dossier:	(For National Authority Use Only)
Name of Product: BGS649		
Name of Active Ingredient: 4,4'-[fluoro-(1-H-1,2,4-triazol-1-yl)methylene]bisbenzotrile	Volume: Page:	

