Due to the potential for dehydration to affect Haematocrit, subjects should be fully hydrated at the time of screening and during the trial when the haematocrit is tested, to ensure a reliable result both for study eligibility assessment and the ongoing monitoring (with respect to the haematocrit stopping criterion).

Eligible subjects will be randomised on Day 1 (Baseline) in a 1:1:1:1 ratio to one of the following treatment groups, consisting of three capsules per dose taken weekly:

-
-
-

Once approximately 100 of the overall planned enrolled subjects have completed the Week 4 visit, an interim analysis will be performed by an independent DMC who will review unblinded data and determine whether the criteria for normalisation of testosterone (testosterone within or above normal reference range for healthy adult males according to FDA criteria) were met. The DMC will establish whether an individual arm has met the criteria of $\geq 75\%$ of subjects reaching the normalisation of testosterone, or whether in the opinion of the DMC following unblinded review that when the arm is fully recruited it is expected to achieve a $\geq 75\%$ response at Week 24 (see [Section 13.6](#)). Dosing arms which meet either of these criteria will be deemed effective. For dosing arms deemed to be ineffective, dosing will be stopped and no further randomisation to that arm will be performed. Subjects assigned to ineffective or unsafe arm(s), as determined per the DMC, will be discontinued from the study, will attend Visit 8 (EOT) and will be followed-up for an additional 12 weeks (FU, Visit 11) and will not be eligible for MBGS206 extension study. Recruitment will continue while the interim analysis is ongoing.

The remainder of the randomisation will then continue in a 1:1:1 ratio of remaining active arms versus placebo to the following treatment groups:

During the 24-week treatment period, subjects in the BGS649 groups and the matching placebo group will take the required dose weekly (± 1 day from the time schedule of regular planned dose). The treatment period consists of 24 weekly doses providing therapeutic coverage to week 24 due to long half-life of BGS649. The capsule will be taken orally by the subject with water.

Seminal Fluid Evaluation:

Semen Quality

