Study treatment			X	Once weekly ¹⁹									
Study drug dispensation			X		X	X	X	X	X	X			
Study drug accountability				X	X	X	X	X	X	X			
AE assessment ²⁰		X	X	X	X	X	X	X	X	X	X	X	X
Concomitant medication	X		X	X	X	X	X	X	X	X	X	X	X

- 1 A minimum of 25 subjects per treatment arm will be invited to participate in a 6-month extension study (Protocol MBGS206), starting at Visit 8 (EOT). Subjects participating in the 6-month extension will have their last study visit at Visit 8 (EOT)
- 2 Telephone Assessment Visit only
- 3 Limited physical examination (cardiovascular system and lower extremities oedema)
- 4 Vital signs assessment will include the measurement of SBP, DBP, pulse, oral temperature and body weight
- 5 Fasting transferrin
- 6 A microscopic examination including RBC and WBC will be performed only when dipstick evaluation is positive for WBC and/or blood or protein
- 7 All blood samples are to be collected after 8 hours fasting, after ECG and vital sign measurements
- 8 Bone turnover markers include CTx1, osteocalcin, bone alkaline phosphatase and PINP
- 9 At Screening serum total testosterone concentration must be < 300 ng/dL (10.4 nmol/L) based on two morning samples, taken before 11 am at least 3 days apart. Laboratory parameters from screening visit 1 do not need to be received before screening visit 2 is take place
- 10 Oestradiol and LH will not be measured at this visit
- 11 Samples to be collected in the morning before 11 am pre-dose
- 12 Semen quality analysis will include semen volume, sperm count, concentration, motility and morphology. Sample collection is not required to be the same day as the assessment visit. Therefore sample collection is allowed within +/-48 hours the scheduled visit for Baseline and attendance Visits during the treatment phase
- 13 Semen samples for seminal fluid PK is not required to be the same day as the assessment visit. Therefore semen PK collection is allowed +/- 48 hours around the attendance visits
- 14 Samples will be taken at pre-dose and 1h post-dose for sparse plasma PK sampling at Visit 5 (week 12). Investigators should ensure that Visit 5 where plasma PK is measured coincides with the study drug dosing day. At EOT Visit 8 (Week 24), PK will be taken only once together with other laboratory assessments taken at that visit.
- 15 Subjects should come well hydrated, drinking water the night before and the morning before the impedance measurements

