7.1.4.2 Treatment Compliance

Duration of Exposure

The duration of Exposure to study medication (number of days) will be defined as:

(date of last dose of study medication – date of first dose of study medication) + 1

Treatment Compliance

Overall treatment compliance will be defined as:

$$\frac{100\% \times [\text{Total Number of capsules dispensed} - \text{Total Number of capsules returned}]}{[(\text{Duration of Exposure (weeks)} \times \text{Number of capsules expected to be taken (3)})]}$$

Where Duration of Exposure (weeks) = [duration of exposure (days) / 7] rounded up to the nearest integer to derive the number of weeks started medication.

If either the duration of exposure is missing or the number of (Number of capsules dispensed – Number of capsules returned) cannot be calculated then the compliance calculation will not be computed.

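### The compliance formula drops one expected week when the last dose is taken a day early, and does not say whether capsules dispensed at Visit 8 count

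*SAP*

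**What the plan says.** **Formula.** SAP 7.1.4.2 defines exposure in days as "date of last dose of study medication – date of first dose of study medication) + 1". That figure is divided by seven and "rounded up to the nearest integer to derive the number of weeks started medication". Compliance is 100 times (capsules dispensed minus capsules returned) divided by (weeks times three capsules). The numerator has no closing visit.

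**Dosing.** The Protocol synopsis says "All subjects will be treated with BGS649 or matched placebo for a maximum of 24 weekly doses", and Protocol 9.1.1 adds: "The treatment period consists of 24 weekly doses providing therapeutic coverage to week 24 due to long half-life of BGS649". The same section tells subjects to "take the required dose weekly (± 1 day from the time schedule of regular planned dose").

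**Supply.** In Protocol Table 9-1 the row "Study drug dispensation" is marked at Visits 1, 3, 4, 5, 6, 7 and 8. The accountability row is marked at Visits 2 to 8 and not afterwards. Under Protocol 9.1.1 the extension study MBGS206 starts at Visit 8.

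**Use.** SAP 8.5.2 presents overall compliance in the Safety population, with counts of subjects below 80% and above 120%. SAP 6.3 makes sufficient compliance a per-protocol criterion but gives no percentage.

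**The concern.** The rounded-up figure is meant to count dosing weeks begun. It does so when the last dose is on time or late. When the last dose is one day early, the exposure is an exact multiple of seven, nothing is left to round up, and the week of that last dose is lost from the denominator while its capsules stay in the numerator.

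The numerator raises a separate question. The 24th dose precedes Visit 8, yet dispensing is marked at Visit 8 and no later visit in this study could record a return. SAP 7.1.4.1 (adverse events) and 7.1.4.3 (medications) both state what happens at entry to the extension. The compliance definition between them does not.

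At stake is the accuracy of the two counts in SAP 8.5.2. Some subjects could be placed on the wrong side of 80% or 120% although they dosed within the permitted window.

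**Working it through.** **Inputs**
- 24 weekly doses, nominally on Days 1, 8, …, 162, because 1 + 7 × 23 = 162 (Protocol synopsis and 9.1.1).
- Window of ±1 day, so the last dose may fall on Day 161, 162 or 163 (Protocol 9.1.1).
- Three capsules per dose, so 72 for a full course (SAP 7.1.4.2).
- Cut-offs of 80% and 120% (SAP 8.5.2).

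**The plan's own figure.** On schedule, 162/7 = 23.14, rounded up to 24 weeks. Expected capsules are 24 × 3 = 72, and 72/72 = 100%. This agrees with the 24 planned doses.

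**Full course, last dose shifted**
- Day 163: 163/7 = 23.29, rounded up to 24; 72/72 = 100%.
- Day 161: 161/7 = 23 exactly; 23 × 3 = 69; 72/69 = 104.3%.

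**General case.** If the last dose is number k and is one day early, exposure is 7(k − 1) days, so the formula gives k − 1 weeks. Compliance is multiplied by k/(k − 1). For a man who took every dose up to k, it reads:
- k = 24: 24/23 = 104.3%
- k = 12: 12/11 = 109.1%
- k = 6: 6/5 = 120.0%, not above the cut-off
- k = 5: 15/12 capsules = 125%
- k = 2: 2/1 = 200%

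From rounding alone, a perfect course is therefore wrongly counted above 120% only when the last dose is number 2 to 5.

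**Effect at 80% over 24 doses.** True compliance is below 80% when capsules taken are fewer than 0.80 × 72 = 57.6, so 57 or fewer. With an early 24th dose the formula reads 80% or more from 0.80 × 69 = 55.2, so 56 or more. Only 56 and 57 capsules change side:
- 56: 56/72 = 77.8% reads 56/69 = 81.2%.
- 57 (19 whole doses): 57/72 = 79.2% reads 57/69 = 82.6%.
- By comparison, 54 (18 whole doses): 54/72 = 75.0% reads 54/69 = 78.3% and is still counted below 80%.

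**Visit 8 supply (conditional).** Supplies from Visits 1 and 3 to 7 span six four-week intervals, which is 24 doses. The documents give no Visit 8 quantity. I assume 0 to 12 capsules, the upper end being four weeks × 3, and no return in this study.
- 0 capsules: no effect.
- 12 capsules, full course, last dose on time: 84/72 = 116.7%, an excess of 16.7 points.
- 12 capsules, 16 of 24 doses: 48/72 = 66.7% reads 60/72 = 83.3%. True compliance from 46 to 57 capsules (63.9% to 79.2%) reads 80% or more.
- 12 capsules and an early last dose, full course: 84/69 = 121.7%, counted above 120%.

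**Check of the repair.** Use expected doses = round((last dose date − first dose date)/7) + 1. For last doses on Days 161, 162 and 163 the differences are 160, 161 and 162 days. Divided by seven these are 22.86, 23.00 and 23.14; all round to 23, giving 24 doses. The same rule returns k for every k from 1 to 24 with the last dose one day early, on time or one day late.

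**The case against.** The rounding error has a narrow reach. It needs a last dose exactly one day early. Over a full course it changes the below-80% count only for men at 56 or 57 capsules, and a fully compliant man at 104.3% trips neither cut-off. That is correct and sets the size of the point. It does not remove the point, because the case arises from dosing that the protocol allows.

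On Visit 8, the natural reading is that the mark refers to extension supply, since MBGS206 begins at that visit and treatment in this study is capped at 24 doses. Packaging details are redacted, and the SAP's copy of the schedule is not legible on this row in the text available. A reader might infer that Visit 8 capsules do enter the compliance ratio. The documents do not show that, so this part stands only as a conditional.

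A reader might also infer that the per-protocol set is affected. SAP 6.3 states no threshold and leaves detail to the classification meeting plan. SAP 6.6 has exclusions decided at that meeting from listings and deviation logs, among other sources. Protocol 10.4 also uses the subject's interview and has intake dates and times recorded. No text ties the 80% or 120% cut-offs to per-protocol membership.

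**Conclusion.** The rounding rule gives a wrong denominator for an early last dose. This follows from the documents with no outside assumption. The error is minor: 4.3 points for a full course, larger for men who stop early, and enough to put a perfect course ending at doses 2 to 5 above 120%.

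It would be too strong to say that the errors simply conceal non-compliance. Some men below 80% are missed, but some fully compliant men are falsely counted above 120%.

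The Visit 8 overstatement is 0 to 16.7 points for a full course. It depends on an assumed 0 to 12 capsules being logged in this study and not returned. Any effect on the per-protocol set cannot be determined without a stated threshold. The primary analysis uses the ITT population with LOCF (SAP 8.6.2), and compliance is not part of ITT membership (SAP 6.1), so it does not change.

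**What to change.** 1. In SAP 7.1.4.2, replace the rounded-up weeks with expected doses = round((date of last dose − date of first dose)/7) + 1, and keep the factor of three capsules. This is one line of text and one of code, and uses dates already in the formula. It keeps the SAP's choice to end the expected period at the last dose taken.
2. In the same section, limit capsules dispensed to those issued before Visit 8 (EOT), and state how extension entrants are handled, as SAP 7.1.4.1 and 7.1.4.3 already do. This costs one sentence and a filter on visit.
3. Have the Visit 8 dispensation mark in Protocol Table 9-1 reconciled with the 24-dose maximum, with a statement of which study's accountability records that supply. This needs a short clarification from the sponsor and is the only part that goes beyond the SAP.

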7.1.4.3 Prior, Concomitant and Follow-up Medications/Procedures

Medications and Procedures will be assigned as being prior to study treatment, concomitant with study treatment or taken during the follow-up phase based on the start and stop dates of the medication and dosing dates.

If the medication/procedure stop date is before the date of the first dose of study medication, the medication/procedure will be assigned as being prior to study treatment. Otherwise, the medication/procedure will be assigned as being concomitant with study treatment unless the start date of the medication/procedure is after the Visit 8 date, when it will then be classified as occurring in the follow-up phase. For subjects that enter the extension study, only medications/procedures with a start date prior to entering the extension study will be categorised and summarised.

7.1.4.4 Osteopenia and Osteoporosis

DXA Scans assessments for each region (Spine and Hip) will be assigned into the below severity categories:

- Normal: (T score >-1.0)
- Osteopenia: (T Score between -1.0 and -2.5)
- Osteoporosis: (T score < -2.5 or Z-Score (under 50 years) <-2.0)

7.1.4.5 Potential Hy's Law Criteria

Subjects will be deemed as meeting potential Hy's law Criteria if their ALT or AST > 3x ULN and bilirubin > 2 x ULN at the same visit.

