9.3.7 Study Drug Interruption and Discontinuation

Subjects may voluntarily discontinue investigational treatment for any reason at any time.

At the time of study drug discontinuation, the subject should have (as soon as possible) an EOT visit with the assessments that are normally done at the Week 24 visit (this should take place within 7 days of discontinuation of study drug). In addition subjects who discontinue the study drug are expected to complete the 12 week follow-up period (Visits 9, 10 and 11) to collect safety data. Subjects who have discontinued before Week 12 (Visit 5) are not required to have EOT DEXA scan measured. The subjects will in addition provide semen sample for PK analysis at Visits 8 (EOT), unless they are not able to provide the samples. This applies also to a subject discontinued because of elevated testosterone as determined by an unblinded physician and if the whole treatment arm is discontinued because of elevated testosterone level as determined by DMC. The investigator and study staff must discuss with the subject, the subject's continued participation in the study and request subjects to continue attending follow-up visits according to the study visit schedule. A study arm may be discontinued from the treatment at the Week 4 visit as decided by DMC during interim analysis (see [Section 9.1](#)). Discontinued subjects will not be replaced. Those subjects will attend only Visit 8 (EOT) and will be followed at FU-Visits 9, 10 and 11 (to 12 weeks after EOT).

The only exception to this requirement is when a subject withdraws consent for all study procedures including post-treatment study follow-up or loses the ability to consent freely (i.e., is imprisoned or involuntarily incarcerated for the treatment of either a psychiatric or physical illness).

If the subject cannot, or is unwilling to attend the follow-up visits, the site staff should request maintenance of regular phone contact with the subject, or with a person pre-designated by the subject. This phone contact should preferably be performed according to the study visit schedule. Data concerning the subject's health status, including information regarding new/concomitant treatments, AEs, AESIs, i.e., rash and vital status will continue to be collected.

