If the subject decides to completely withdraw from the study (refuses any further study participation or contact) all study participation for that subject will cease and data to be collected at subsequent visits will be considered missing.

The investigator must also contact the IRT to register the subject's discontinuation from investigational treatment.

If study drug is discontinued prior to the subject's completion of the study, the reason for the discontinuation must be documented in the subject's medical records and entered on the appropriate case report form (CRF) page.

If the subject temporarily discontinues study drug because of AE or SAE or other relevant issue, investigator may restart if considered medically safe and in discussion with the Medical Monitor.

Investigational treatment MAY be permanently discontinued under the following circumstances:

1. Significant worsening of lower extremity oedema (demonstrated by use of the same technique of evaluation for comparison over time and which is not due to local pressure /venostasis effects such as may be caused by socks or other clothing).
2. Significant worsening of obstructive urinary symptoms

Investigational treatment MUST be permanently discontinued under the following circumstances:

3. Total testosterone \geq 1500ng/dL (52 nmol/L) at any two consecutive scheduled visits during the study
4. Liver laboratory values of:
 - ALT or AST >5 times the ULN

If the increase in ALT or AST, is associated with normal bilirubin and ALP, the medical evaluation of withdrawing a patient can be made on a repeat AST/ALT test taken within 48 hours. (Repeated parameters should include: ALT, AST, Alkaline phosphatase and total bilirubin). The subject should interrupt study drug until the repeat liver enzymes are available. If repeat liver parameters are all within the normal range, dosing may be continued. If not normalised the subject should be permanently discontinued.

or

- ALT or AST >3 times the ULN and bilirubin total >2 times ULN or International Normalised Ratio (INR) >1.5 or the appearance of worsening fatigue, nausea, vomiting, right upper quadrant pain/tenderness, fever, rash, or eosinophilia.
 - A hepatic event leading to subject discontinuation should be followed up until event resolution, or becomes not clinically significant
5. Any of the following laboratory abnormalities:
 - Renal function values that require discontinuation:

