8.7.2 Laboratory evaluations

8.7.2.1 Clinical laboratory

Haematology, blood chemistry, and urinalysis assessments will be conducted at Screening, Baseline, each visit during the treatment phase and Week 36.

The following laboratory parameters will be assessed:

- Blood chemistry
 - Sodium
 - Potassium
 - Chloride
 - Bicarbonate/CO₂
 - Blood urea nitrogen

-
- Creatinine
 - Fasting Glucose
 - Albumin
 - Alkaline phosphatase
 - AST
 - ALT
 - GGT
 - PT/INR
 - Total bilirubin
 - Total protein
 - Calcium
 - Lipid panel (total cholesterol, LDL, HDL, triglycerides)
 - PSA
 - eGFR (calculated based on Cockcroft-Gault formula)
 - eGFR (derived from 4-v MDRD)
 - Haematology
 - Red Blood Cell Count [RBC]
 - White Blood Cell Count [WBC]
 - Neutrophils
 - Lymphocytes
 - Monocytes
 - Eosinophils
 - Basophils
 - Haemoglobin
 - Haematocrit
 - Platelets
 - Urinalysis
 - Specific gravity
 - pH
 - Protein
 - Bilirubin
 - Glucose
 - Blood
 - Ketones
 - Leukocytes

For the purposes of summarisation in both the tables and listings, all clinical laboratory data will be reported in Standard International (SI) units.

If a lab value is reported using a nonnumeric qualifier e.g., less than (<) a certain value, or greater than (>) a certain value, the given numeric value will be used in the summary statistics, ignoring the nonnumeric qualifier.

Descriptive statistics will be presented for quantitative clinical laboratory parameters for each treatment regimen and time-point. Similarly, changes from baseline (and changes from screening for selected renal parameters; creatinine, urea, and glomerular filtration rate) will be summarised.

The change from baseline in each renal parameter to Week 24 will also be analysed via MMRM in the same manner as the change from baseline in total testosterone (see Section 8.6.3.1).

Values outside the normal range will be categorised as H (above the normal range) or L (below the normal range) based on the laboratory's reference range and these will be flagged in the individual data listings along with the Investigator's assessment.

In addition boxplots of observed values by treatment and visit will be generated for the below lab parameters:

- Hematocrit
- Hemoglobin
- Creatinine
- PSA

Qualitative urinalysis parameters (e.g protein, glucose and blood) will only be listed.

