8.7.2.3 Liver Function

The number and proportion of subjects with laboratory values for liver function and enzymes of clinical concern as follows will be presented descriptively by treatment regimen:

Parameter	Level for clinical concern
ALT	> 1.5 times the upper limit of the normal range (ULN) > 2xULN > 3xULN > 5xULN > 10xULN
AST	> 1.5xULN > 2xULN > 3xULN > 5xULN > 10xULN
Bilirubin Total	> 2xULN > 3xULN
ALT/AST and Bilirubin Total	ALT/AST > 3xULN and Bilirubin Total > 2xULN (assessments to occur at the same visit)

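### The SAP's combined potential Hy's law count requires both elevations at one visit, so it misses a man whose bilirubin first passes 2×ULN after ALT and AST have both fallen to 3×ULN or below

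*SAP*

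**What the plan says.** SAP 7.1.4.5 sets the derivation: a subject meets the potential Hy's law criteria with "ALT or AST > 3x ULN and bilirubin > 2 x ULN at the same visit". SAP 8.7.2.3 puts this into a descriptive table of subject counts by arm. ALT and AST each have rows that include >3×ULN, total bilirubin has rows for >2×ULN and >3×ULN, and one combined row carries the same limit: "assessments to occur at the same visit".

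The protocol's liver criterion in 9.3.7 uses the same two thresholds, with alternatives to bilirubin: "ALT or AST >3 times the ULN and bilirubin total >2 times ULN or International Normalised Ratio (INR) >1.5", or listed symptoms and signs. It sits under the heading "Investigational treatment MUST be permanently discontinued under the following circumstances", does not use the term Hy's law, and says nothing on whether the values must come from one visit.

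On timing, SAP 8.7.2.1 states: "Haematology, blood chemistry, and urinalysis assessments will be conducted at Screening, Baseline, each visit during the treatment phase and Week 36". Protocol 9.3.7 adds an EOT visit after early stopping ("this should take place within 7 days of discontinuation of study drug"). For ALT or AST above 5×ULN with normal bilirubin and alkaline phosphatase, it allows a repeat liver panel within 48 hours. SAP 8.1.7 lists unscheduled results but keeps them out of tables.

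**The concern.** In a liver injury the transaminases and bilirubin need not peak on the same day. If bilirubin crosses its threshold at the next sample, when the transaminases have already come down, neither visit holds the qualifying pair. Here the next sample may be a separate EOT visit up to 7 days later, or the next scheduled visit about 4 weeks later. Stopping or interrupting drug gives the transaminases time to fall, while exposure continues because the elimination half-life is given as 21 days (Protocol 9.2).

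The combined row is the only place where the SAP brings the two elevations together, and no hepatic event is among the adverse events of special interest in Protocol 12.1.7. The separate rows are counts per arm: one man in the ALT >3×ULN row and one in the bilirubin >2×ULN row could be the same man or two different men. A zero in the combined row could then be read as no potential case when a sequential one had occurred.

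**Working it through.** There is no published figure to reproduce, so the check is of the rule itself.

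**1. Spacing of scheduled chemistry** (Protocol Table 9–1). Visits are at Baseline, Day 8, Weeks 4, 8, 12, 16, 20, 24 and 36. Successive gaps are 7, 21, 28, 28, 28, 28, 28 and 84 days. From Week 4 to Week 24 each visit has a window of ±2 days, so consecutive visits can be 28 − 2 − 2 = 24 to 28 + 2 + 2 = 32 days apart.

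**2. The rule on assumed values.** Each pair is (higher of ALT and AST, total bilirubin) in ×ULN at two successive assessments. The values are illustrative, not from the documents.

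| Pattern | First | Second | Same-visit rule | Any-visit rule |
|---|---|---|---|---|
| A: bilirubin later, transaminases back to ≤3 | (4, 1) | (2.5, 2.5) | not counted | counted |
| B: bilirubin later, transaminases still >3 | (4.5, 1) | (3.5, 2.5) | counted | counted |
| C: both at one visit | (4, 2.5) | (1, 1) | counted | counted |
| D: bilirubin first | (1, 2.5) | (4, 1) | not counted | counted |

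In all four patterns the man enters both the >3×ULN transaminase row and the >2×ULN bilirubin row. A later bilirubin rise is lost from the combined row only in pattern A.

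**3. A route to pattern A through the protocol's own steps.** Suppose ALT is 6×ULN with bilirubin 1.5×ULN at Week 8. Bilirubin is not normal, so the 48-hour repeat route in Protocol 9.3.7 does not apply; the man stops drug and attends EOT within 7 days. If EOT then shows ALT 2.8×ULN, AST no higher than 3×ULN and bilirubin 2.5×ULN, both thresholds have been passed within about a week and the pair is met at neither visit. The AST condition is needed: with AST above 3×ULN at EOT he would be counted.

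**4. Repeat panels.** The 48-hour repeat measures ALT, AST, alkaline phosphatase and total bilirubin together, so it supplies its own pair. Under a same-visit rule it fails to qualify only if the transaminases have dropped from above 5×ULN to 3×ULN or below. Even a qualifying pair would stay out of the table if the panel is treated as unscheduled under SAP 8.1.7. That is a second, separate cause of omission.

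**5. Window length.** A 30-day window falls short of the largest on-treatment gap (30 < 32). A window of 32 days reaches the next on-treatment visit in every case. It does not span Week 24 to Week 36 (84 days).

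**The case against.** A same-visit pair is explicit and reproducible, and it is used descriptively as a screen for potential cases. Pattern A needs the transaminases to fall to 3×ULN or below while bilirubin is still rising, and nothing in the documents says how often that happens. This stands: the gap is narrow and its frequency unknown.

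Three stronger readings are tempting, and the documents do not support them.

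- *Every man whose bilirubin rises after his transaminases is missed.* No. Pattern B is counted; only men with both ALT and AST at or below 3×ULN at the later assessment are lost.
- *The SAP contradicts the protocol.* No. Protocol 9.3.7 is a discontinuation rule for the individual and is silent on timing. It neither requires one visit nor says that values from different visits may be combined. The SAP adds a restriction to an analysis definition that the protocol does not give.
- *The man disappears from the report.* No. He is in the single-parameter rows. Listings are by subject and date and include unscheduled results (SAP 8.1.7), with out-of-range values flagged (SAP 8.7.2.1). An abnormality leading to discontinuation is reportable as an adverse event (Protocol 12.1.4), and such events are tabulated and listed (SAP 8.7.1). The DMC also reviews unblinded safety data (SAP 8.8.1).

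These safeguards allow a careful reader to find him. They do not classify him, and they do not correct the combined count.

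A date-based rule also has a cost in specificity. Protocol 9.3.2 admits men whose raised screening bilirubin is due to Gilbert syndrome, and a fluctuating bilirubin could be paired with a transaminase rise that has already resolved. This is a reason to flag such men and keep both rows.

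**Conclusion.** The point holds in its narrow form. The combined count omits a man whose bilirubin first exceeds 2×ULN at a later assessment at which ALT and AST are both at or below 3×ULN, and the per-arm single-parameter rows cannot show that the two rises belong to one man. It is an unexplained restriction in the SAP, not a conflict with the protocol.

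The size cannot be put in numbers. The planned active-arm total is 3 × 67 = 201 men, the documents give no rate for these events, and the men missed are a subset of what is likely to be very few. The case for change rests on the seriousness of the signal, on data already being collected, and on the small cost. It assumes only that pattern A can occur, which the visit spacing and the EOT visit allow.

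**What to change.** In SAP 7.1.4.5 and 8.7.2.3:

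- Keep the same-visit row as written.
- Add a second row counting any subject with a total bilirubin >2×ULN after first dose, dated on or after an ALT or AST >3×ULN also after first dose, within a pre-specified window. Set the window to at least 32 days so that it reaches the next on-treatment visit. The length is an assumption, since the documents give none.
- Build the row on assessment dates, not visit labels. Include unscheduled, repeat and EOT samples, stated as an exception to SAP 8.1.7.
- List every subject counted in either row, with all ALT, AST and total bilirubin values and dates, and flag Gilbert syndrome or raised baseline bilirubin.

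Pattern D, where bilirubin rises first, stays outside the new row by construction. A rise after Week 24 is caught only if a sample falls inside the window.

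The cost is SAP wording, a merge by date in place of one by visit, and a few extra men flagged for review. No assessment is added and no stopping rule changes.
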